12.1 Study Design/Endpoints

We will collect data on physical function, patient-reported outcomes, decision parameters, patient activation, and attitudes toward deprescribing.

12.2 Sample Size/Accrual Rate

We plan to enroll one subject/month for 16 months.

12.3 Stratification Factors

Not applicable

12.4 Analysis of Endpoints

12.4.1 Analysis of Endpoints

The study team will compare the On-arm to the Off-arm for the 4 main outcomes of interest—vitals collected via remote monitoring, step-count, peak oxygenation uptake, short physical performance battery score, and patient-reported outcome domains. To achieve this, analysis will use a general linear mixed effects model, where fixed effects of BB, period effect (Period 1 or Period 2) and carry-over effect will be included. In addition, a patient-level random intercept will be added to the model to account for within-patient repeated measurements. To control for inflation of Type I error due to testing multiple outcomes, the Holm's stepdown procedure will be used. The overall Type I error will be set at 5% and all statistical analyses will be two-sided.

1. *Vitals collected via Remote Monitoring.* A general linear mixed effects model will be used, comparing daily pulse and blood pressure averages of the On and Off arms. The study team will analyze data from the timeframe during which BB is completely stopped (“Off” when participating in the Off-arm) and at usual dose (“Full dose” when participating in the On-arm); this will occur during the last 2 weeks each Period (see Figure 1). The study team will utilize a general analytic framework to analyze average blood pressure and pulse during each period.
2. *Physical activity (via step-count).* A general linear mixed effects model will be used, comparing daily step-count averages of the On and Off arms. The study team will analyze data from the timeframe during which BB is completely stopped (“Off” when participating in the Off-arm) and at usual dose (“Full dose” when participating in the On-arm); this will occur during the last 2 weeks of each Period (see Figure 1). The study team will utilize a general analytic framework to analyze average daily step-count during each period. As an exploratory analysis, the study team will also perform analysis that will visualize and test the pattern of activity as a function of time in specialized statistical models called functional data model developed for this purpose. The study team will then test the differences in the properties of these curves between the two treatment groups.
3. *Function (via short physical performance battery).* A general linear mixed effects model will be used, comparing the short physical performance battery score of the On and Off arms.

4. *Exercise capacity (via peak oxygen consumption during exercise).* A general linear mixed effects model will be used, comparing VO2 of the On and Off arms.
5. *Patient-reported outcomes (PROs).* A general linear mixed effects model will be used, comparing each patient-reported outcome domain (HF-specific quality of life, fatigue, depression, anxiety, sleep, physical function, social role, and pain) of the On and Off arms. The study team will analyze data from the timeframe during which BB is completely stopped (“Off” when participating in the Off-arm) and at usual dose (“Full dose” when participating in the On-arm); this will occur during weeks 5 and 6 of each Period, or the last two weeks of the period. (see Figure 1).
6. *Subject Qualitative Interviews.* Directed content analysis methods will be used to develop relevant categories and themes from interview transcript data. Coding will be conducted through the coding platform Dedoose. Transcripts will be analyzed by two team members, consulting additional members to establish consensus where needed. Inter-rater reliability between coders will be established using a Cohen's Kappa score.

To provide statistics to the subjects when sharing key outcomes, we will compare PROs between Periods A (On) and Periods B (Off) using a linear or generalized linear mixed effects model that will include the fixed effects of beta-blocker, treatment effect (A vs B), period effect (1, 2, 3, 4 etc.) and a patient-level random intercept to account for within-patient repeated measurements. The period fixed effect will estimate the effects of down-titration/up-titration and the time-dependent treatment effect will estimate On vs. off effect. We will also explore period-specific fixed effects for treatment and compare the models using Akaike Information Criterion. As an exploratory analysis, we will also test the pattern of activity as a function of time in specialized statistical models called functional data model.

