For patients in Arm 1, the number of periods a subject will complete is dependent on their decision about continuing or discontinuing their beta-blocker at their end of period 2 or end of period 3 visit. If a subject decides they would like to continue their beta-blocker after period 2, they will complete a period 3 to allow for safe up-titration. End of period visits, including the end of intervention period, may be conducted either remotely or in person, based on subject preference and the current status of the COVID-19 pandemic. End of period and end of intervention visits conducted remotely will not have the following physical assessments associated with it: Cardiopulmonary Exercise Test, Short Physical Performance Battery, blood draw, physical assessment, six-minute walk test, and an EKG. Subjects in Arm 1/ABAB who want to stop their beta-blocker can complete their end of intervention visit at period 2 and enter follow-up.

Test, Short Physical Performance Battery, blood draw, physical assessment, six-minute walk test, and an EKG. Subjects in Arm 1/ABAB who want to stop their beta-blocker can complete their end of intervention visit at period 2 and enter follow-up.

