Subjects randomized into Arm 2/BABA will start with Off[B]. Instead of abruptly stopping beta-blocker, these subjects will have their previously prescribed home beta-blocker dose reduced by 50% each week, until the subject is completely off beta-blocker. During Period 2, they will restart beta-blocker by starting a low dose and then doubling this dose every week until reaching their home dose. During Period 3, we will again conduct a dose reduction, reducing each dose by 50% for a week, until the subject is off of beta-blockers. Finally, they will restart beta-blocker by starting a low dose and then doubling this dose every week until reaching their home dose (Similar to Period 2). See Figure 1 above. Regarding patients in Arm 2, if a subject decides they would like to stop their beta-blocker after period 2, they will complete a period 3 to allow for safe down-titration. End of period visits, including the end of intervention period, may be conducted either remotely or in person, based on subject preference and the current status of the COVID-19 pandemic. End of period and end of intervention visits conducted remotely will not have the following physical assessments associated with it: Cardiopulmonary Exercise Test, Short Physical Performance Battery, blood draw, physical assessment, six-minute walk test, and an EKG. Subjects in Arm 2/BABA who want to continue their beta-blocker can complete their end of intervention visit at period 2 and enter follow-up.

We will incorporate an adaptive study design, where each subject will have the option to participate in less (2-3) or more periods (5-6) depending on whether they need additional information to make an informed decision about continuing or discontinuing their beta-blocker at the end of this trial.

Subjects will wear a Garmin wearable device for the duration of the study to collect data on step count to quantify physical activity. We may collect additional data that is captured by the wearable devices, such as floors climbed, distance traveled and calories burned. We may eliminate the use of wearable devices per subject feedback.

Subjects will also undergo a non-invasive cardiopulmonary exercise test (CPET) at the end of period 1 and at the end of period 2 to assess exercise parameters including peak oxygen consumption. In

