addition, they will undergo the short physical performance battery at baseline and at the end of each intervention period. The study team will discuss the components of the CPET with the subjects prior to their end of period visits.

Through a pre-existing remote monitoring program at Weill Cornell Medicine, we will provide subjects with a computer tablet and blood pressure cuff free-of-charge. This will allow us to collect vital sign data, including blood pressure and heart rate. We will encourage subjects to collect data up to 3 times per week. Based on patient reports of any concerning symptomatology, we may encourage increased frequency of assessments at different time points of the study. Also, based on prior experience, some subjects may want to collect data more frequently, which will allow. This approach was developed based on our preliminary data from 9 prior N-of-1 trials, where there were no serious adverse events and based on subject feedback (Several subjects requested reduced frequency of required vital sign assessment). If we encounter “Red Flags” (Table 3), we will call the subject to assess symptoms and determine the need for medical attention and/or study withdrawal.

Table 3. Red Flags triggering phone call

| | Upper Limit | Lower Limit |
|--------------------|--------------------|--------------------|
| Blood Pressure | >160/90 mmHg | <100/60 mmHg |
| Resting Heart Rate | >100 bpm | <60 bpm |

Remote monitoring will occur on a daily basis. Subjects will be provided with a tablet computer and blood pressure cuff free-of-charge. These data will be automatically uploaded to an online portal, which we will review weekly.

Subjects will complete subject-reported outcome questionnaires on quality of life, cognitive function, and sexual function at regular intervals set by each of the validated instruments during the intervention stage via their tablet computers, over the phone, or via email.

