11.2.5 Record Retention

Essential documents are those documents that individually and collectively permit evaluation of the study and quality of the data produced. After completion of the study, all documents and data relating to the study will be kept in an orderly manner by the Investigator in a secure study file.

12. Statistical Considerations

To provide statistics to the subjects when sharing key outcomes, we will compare PROs between Periods A (On) and Periods B (Off) using a linear or generalized linear mixed effects model that will include the fixed effects of beta-blocker, treatment effect (A vs B), period effect (1, 2, 3, 4 etc.) and a patient-level random intercept to account for within-patient repeated measurements. The period fixed effect will estimate the effects of down-titration/up-titration and the time-dependent treatment effect will estimate On vs. Off effect. We will also explore period-specific fixed effects for treatment and compare the models using Akaike Information Criterion. As an exploratory analysis, we will also test the pattern of activity as a function of time in specialized statistical models called functional data model.

Power: The study team will have 80% power to detect a within-patient difference of 1.1 standard deviations in the four outcomes at an $\alpha=1.67\%$ (after controlling for Type I error inflation due to three outcomes). While power for these analyses will be modest, they will provide pilot data necessary for a future proposal to the National Institute of Health (NIH) and/or Patient-Centered Outcomes Research Institute (PCORI) to conduct a larger multi-center randomized controlled trial to determine whether discontinuation of BB in HFpEF can improve outcomes relevant to older adults including function and quality of life.

Power: The co-primary objective is to determine features of a feasible and pragmatic protocol for deprescribing N-of-1 trials, which will be done through an iterative stakeholder-engaged process (C.1.2). The goal is *not* to establish safety and/or efficacy here. Thus, power calculations for this Aim are less relevant.

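### The group On/Off model in 12.4.1 has a two-level period term, but every outcome except peak VO2 is collected over 2 to 6 periods, so Periods 3 and later must be dropped or misfitted

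*Combined protocol and SAP*

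**What the plan says.** The lead-in to 12.4.1 sets out a general linear mixed model for vitals, step count, peak VO2, SPPB and the PRO domains, "where fixed effects of BB, period effect (Period 1 or Period 2) and carry-over effect will be included", with a patient-level random intercept.

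Section 3.1 describes ABAB or BABA sequences with at least two periods, four as the standard scheme, and an option of 2-3 or 5-6. On SPPB it says "they will undergo the short physical performance battery at baseline and at the end of each intervention period" (visits held remotely omit it). Section 12.4.1 takes step count, vitals and PROs from the last two weeks of each period. Peak VO2 is measured only at the ends of Periods 1 and 2 (3.1 and the Schedule of Assessments).

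The exit rules in 3.1 differ by arm. For Arm 1, "Subjects in Arm 1/ABAB who want to stop their beta-blocker can complete their end of intervention visit at period 2 and enter follow-up". The Arm 2 rule is that "if a subject decides they would like to stop their beta-blocker after period 2, they will complete a period 3 to allow for safe down-titration". The mirror rule applies to subjects who choose to continue: Arm 1 adds a Period 3, and Arm 2 can finish at Period 2.

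A second model, in Section 12 and again at the end of 12.4.1, has a "period effect (1, 2, 3, 4 etc.) and a patient-level random intercept to account for within-patient repeated measurements". Its stated purpose is to give subjects statistics on their PROs. It lists no carry-over term.

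**The concern.** Two levels match the data for peak VO2 and for nothing else in the list. For step count and SPPB, both co-primary, and for vitals and PROs, an analyst following the text has to choose. One choice is to discard Periods 3 and later. The other is to squeeze them into two levels, either by position within each On/Off cycle or as Period 1 versus all later periods. The plan selects none of these.

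Dropping the later periods gives up the repeat crossover, which is the main reason for running more than one On/Off pair. Squeezing them into two levels means that a trend over time (test practice, season, disease course) is not fully removed and can enter the On-Off contrast. The study is unblinded and outcomes are analysed for each DSMB meeting (12.5). If the choice stays open, it could be made after results are known.

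**Working it through.** **Plan's own figure.** The only computable figure nearby is the power statement in Section 12: 80% for 1.1 SD at alpha 1.67%. The alpha reproduces (5%/3 = 1.67%). The power does not reproduce if the SD is that of the within-patient difference: N=16 then gives 93.8% (crossover t, df 14). About 80% needs an unstated assumption, such as 1.1 SD of a single measurement with correlation about 0.25. This is a separate matter, and nothing below depends on it.

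**Inputs.** From the documents: N=16, 1:1 allocation, 2 to 6 periods, and the exit rules in 3.1. Assumed, because the documents give no values: residual SD s per period, between-patient SD t of the treatment effect, intraclass correlation (ICC), drift g per period, and exit patterns.

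**(a) Dropping Periods 3-4 when all 16 subjects complete four periods.**

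Without carry-over, SE = sqrt(2s² + t²)/4 from Periods 1-2 and sqrt(s² + t²)/4 from all four. With s = 1:

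| t | Periods 1-2 | All four | Ratio |
|---|---|---|---|
| 0 | 0.354 | 0.250 | 1.41 |
| 0.5 | 0.375 | 0.280 | 1.34 |
| 1.0 | 0.433 | 0.354 | 1.22 |

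For 80% power at two-sided alpha 1.67% (noncentral t, df 14), the detectable difference is 0.90 SD of a one-pair difference from Periods 1-2. From all four periods it is 0.64, 0.67 or 0.74 (0.90 divided by each ratio).

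With a carry-over term, total variance 1 and t = 0, two periods identify the effect only from the Period 1 comparison between arms: SE = sqrt(1/8 + 1/8) = 0.500. With four periods, variance = (s²/4)(3 - w)/(3 - 4w), where w = ICC/(s² + 4·ICC) and s² = 1 - ICC.
- ICC 0.5: w = 0.2, variance = 0.125 × 2.8/2.2 = 0.159, SE = 0.399, ratio 0.500/0.399 = 1.25.
- ICC 0.7: w = 0.226, variance = 0.075 × 2.774/2.097 = 0.099, SE = 0.315, ratio 1.59.

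**(b) Dropping later periods when exits are early (no carry-over, t = 0).** The illustrative pattern takes Section 2.3.3's 8 of 9 patients who felt better off the drug as the share who stop. That gives 7 AB and 1 ABA in Arm 1, and 7 BAB and 1 BA in Arm 2. The SE is 0.354 from Periods 1-2 against 0.340 from all data (units of s), a ratio of 1.04. If half of each arm stays for four periods (4 AB, 4 ABAB; 4 BAB, 4 BABA), the ratio is 1.25.

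**(c) Keeping later periods under two levels.** A hand case shows the mechanism. Suppose every Arm 1 subject has AB and every Arm 2 subject has BAB, drift is g per period, there is no true effect, and coding is first/second of cycle. Within subjects, Arm 1 gives Off minus On = g = -d + p, where d is the On-Off estimate and p the period estimate. Arm 2 gives On minus the mean of its two Offs = 2g - (g + 3g)/2 = 0 = d + p. Hence p = g/2 and d = -g/2. The random-intercept fit at ICC 0.5 gives about -0.52g.

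The same generalised least squares fit at ICC 0.5 gives these biases in On-Off:

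| Exit pattern | Period coding | No carry-over | Carry-over coded ±1 | Carry-over coded 0/1 |
|---|---|---|---|---|
| 8-of-9 | cycle | -0.39g | +0.71g | +0.92g |
| 8-of-9 | Period 1 v later | -0.19g | +0.35g | +0.35g |
| Half stay | cycle | -0.20g | +0.39g | +1.19g |
| Half stay | Period 1 v later | about -0.06g | +0.12g | +0.12g |
| All complete four | cycle | 0 | 0 | +1.43g |
| Any of these | one level per period | 0 | 0 | 0 |

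For an assumed g of 0.1 to 0.3 SD, the 8-of-9 pattern gives -0.04 to -0.12 SD with cycle coding and no carry-over (0.39 × 0.1 and 0.39 × 0.3). With carry-over, across both codings, it gives +0.04 to +0.28 SD (0.35 × 0.1 and 0.92 × 0.3).

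**The case against.** The strongest defence is that the two-level term was meant literally, as a Periods 1-2 analysis. Two periods are the minimum, later ones are optional, CPET is done only in that block, and it is the one block that all subjects share by design. Such an analysis is unbiased. With early exits it also costs little: 4% in SE in the 8-of-9 pattern. This stands as a defence of that analysis, but the plan nowhere says that it is intended, and 12.4.1 takes step count, vitals and PROs from each period.

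A reader might infer that the two period codings are two rival models for the same comparison. The documents do not support that. The fuller model has its own purpose, feedback to subjects on PROs, and there is no second model for step count, SPPB or vitals. The conflict is between the two-level term and the 2 to 6 period design.

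A reader might also infer that the bias favours Off, the direction that the investigators hypothesise. That follows only if the carry-over term in the quoted model is left out and most subjects choose to stop. Adding carry-over reverses the sign in both unequal-exit patterns tabulated. Without carry-over, the sign also reverses if most subjects continue, and the bias is zero if stoppers and continuers are equal in number, because the Period 3 rules mirror each other. The 8-of-9 figure describes patients who felt better in one physician's practice; it is not a stopping rate for this trial.

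**Conclusion.** The point holds as a gap in specification with a real but variable cost. The text of 12.4.1 cannot be applied to step count, SPPB, vitals or PROs in Periods 3 and later without a choice that the plan does not make.

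- **Precision, if later periods are dropped.** With 16 four-period completers, the SE is 1.41 times larger without carry-over and no variation in treatment effect, which is the ceiling for that case. With carry-over it is about 1.25 times larger at ICC 0.5, and more at higher ICC. It falls to about 1.04 if few subjects go beyond Period 3. Reading 1.41 as the expected loss would overstate it, because some subjects will stop at two or three periods.
- **Bias, if later periods are kept under two levels.** It needs a real time trend, plus either unequal period counts by arm, which the exit rules allow, or a carry-over coding that is not orthogonal to period. Its size and sign depend on exit pattern and carry-over coding, so no direction should be claimed.

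Drift, ICC and exit patterns are assumptions throughout. That one level per period gives zero bias does not depend on their values. Peak VO2 is unaffected.

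**What to change.** In the lead-in to 12.4.1, replace the parenthesis naming Periods 1 and 2 with a categorical period factor that has one level per period observed (Periods 5 and 6 pooled if sparse), using data from all periods, for step count, SPPB, vitals and PROs. Keep two levels for peak VO2 only. State how carry-over is coded, including the value that it takes in Period 1, and to which outcomes it applies. The period term of the subject-feedback PRO model in Section 12 already has the fuller coding and needs no change.

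If a Periods 1-2 analysis is what is intended, say so for each outcome and accept the loss of precision.

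The cost is one or two sentences and two to four more period parameters, with no new data or patients. Pooling Periods 5 and 6 would leave any drift between those two unadjusted. Where only one arm reaches a given period, its own level absorbs those data, so in that case the fuller factor protects against drift without adding precision.

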| Study Description: | We will determine whether N-of-1 trials, as a pragmatic, patient-centered approach to medication optimization that can overcome key barriers of deprescribing, can lead to increased subject confidence regarding the decision to continue or discontinue beta-blockers in older adults with Heart Failure with Preserved Ejection Fraction (HFpEF). |
| Sample Size: | N=16 |
| Enrollment: | This study will enroll 16 subjects. |
| Study Population: | Subjects will be recruited from the HFpEF Program, as well as from the Cardiology, Heart Failure, Geriatrics and/or Internal Medicine clinics at Weill Cornell Medicine. |
| Enrollment Period: | 30 Months |
| Study Design: | This is an unblinded NIH Stage 1 of Behavioral Intervention Development trial, using a Crossover intervention model. We will enroll 16 subjects and we will conduct four rounds of N-of-1 trials with four subjects each. We will use a two-arm crossover titration/reversal design (On [A] vs. Off [B]) with up to 4 periods. Subjects will be randomized to either ABAB or BABA (see Figure 1 below). Each period will last up to 6 weeks, allowing for sufficient time for up-titration and onset of drug action, and down-titration and washout. Each subject will have the option to participate in less (2-3) or more periods (5-6) depending on whether they need additional information to make an informed decision about continuing or discontinuing their beta-blocker at the end of this trial. The intervention drug will be beta-blockers, previously prescribed to the subjects by their physician. We have developed a titration algorithm, where we will reduce the dose of each beta-blocker by 50% every week. |
| Description of Sites/ Facilities Enrolling | |
| Subjects: | Enrollment will only be at Weill Cornell Medicine. |
| Study Duration: | Estimated Primary Completion Date of December 2022 |
| Subject Duration: | 1 Year |
| Study Agent/Device Name | Not applicable |

Intervention Description:

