3.1 Overall Design

This single site, NIH Stage I of Behavioral Intervention Development trial will extend principles of subject-centered care (a pillar of caring for older adults with MCC) to medication management by producing a broadly applicable approach (N-of-1) that can bypass the inherent limitations of randomized controlled trials which provide average treatment effects and limited data on the effects of medication for a single individual; and thereby facilitate personalized pharmacotherapy and therapeutic precision by determining the optimal therapy for the individual in the face of the inherent complexity and heterogeneity of older adults related to variability in clinical phenotype, drug metabolism, responsiveness to therapy, and health priorities.

This study will also formalize a process that can increase subject involvement and incorporate shared decision making into medication management, an important priority in cardiovascular medicine.

We will conduct N-of-1 trials using a two-arm crossover withdrawal/reversal design (On [A] vs Off [B]) with up to 4 periods. Subjects will be randomized to either Arm1/ABAB or Arm2/BABA (see Figure 1 above). After the initial period (Period 1), each subject will crossover to the other arm and continue in that arm for up to 6 weeks (Period 2). This may be repeated for two more periods for a total of 4 periods; each period will last up to 6 weeks, permitting sufficient time for up-titration and onset of drug action, and down-titration and washout. If the subject and the principal investigator make a final decision to discontinue or continue the beta-blocker at the end of a period, the end of intervention phase will begin at the end of that period visit. For the remainder of the protocol, we refer to “end of intervention” as period 4, but this can be changed based on when a final decision is made about the beta-blocker. The end of intervention visits can occur at any of the periods. The minimum number of periods will be 2 (AB or BA). If the subject wishes to collect more data, then additional periods may be added in an alternating fashion (ABAB or BABA). Accordingly, the number of periods will be an adaptive component of the protocol.

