6.1 Schedule of Assessments

| | Baseline | Research Intervention Phase | | | | | Post Intervention Phase | | |
|--|----------|-----------------------------|--------|----------|--------------------|--------------------------------------|-------------------------|-------------------|--------------------|
| | | Daily | Weekly | Biweekly | End of Periods 1-3 | End of Intervention Phase (Period 4) | 6 Month Follow-up | 9 Month Follow-up | 12 Month Follow-up |
| Informed Consent | | | | | | | | | |
| Randomization | | | | | | | | | |
| Demographics | | | | | | | | | |
| Medication Inventory | | | | | | | | | |
| Baseline Beta-Blocker Use | | | | | | | | | |
| Physical Exam | | | | | | | | | |
| Central Blood Pressure | | | | | | | | | |
| Electrocardiogram | | | | | | | | | |
| Cardiopulmonary Exercise Test ² | | | | | | | | | |
| Blood Draw for Troponin & NT-proBNP ³ | | | | | | | | | |
| Blood Draw for Future Research ⁴ | | | | | | | | | |
| Six-Minute Walk Test | | | | | | | | | |
| Short Physical Performance Battery | | | | | | | | | |
| Qualitative Interview | | | | | | | | | |
| Typology Question | | | | | | | | | |
| Health Literacy | | | | | | | | | |
| Number Literacy | | | | | | | | | |
| Short Graph Literacy | | | | | | | | | |
| Data Preferences | | | | | | | | | |
| EQ5d-VAS | | | | | | | | | |
| PROMIS-29 | | | | | | | | | |
| PROMIS-SF 6A | | | | | | | | | |
| PROMIS-Sexual Function | | | | | | | | | |
| KCCQ-12 | | | | | | | | | |

² Cardiopulmonary Test to occur only at the end of Period 1 and Period 2. Cardiopulmonary test to be accompanied by a blood draw for NT-proBNP and Troponin.

³ Blood samples will be collected for Troponin and NT-proBNP at the end of each period. In addition, on visits where the subject performs a Cardiopulmonary Test, we may collect blood for Troponin and NT-proBNP directly after the cardiopulmonary test.

⁴ Optional component of this study. Blood will be drawn at baseline, as well as at the end of Period 1 and Period 2

| | | | | | | | | | | |
|--|---|---|---|--|--|---|---|---|---|---|
| Decision Making Outcomes Questionnaires ⁵ |  | | | | |  | | | | |
| Dose Modification | | |  | | |  |  | | | |
| Telephone Call ⁶ | | |  | | | | | | | |
| Step Count Collection | |  | | | | | | | | |
| Remote Monitoring | |  | | | | | | | | |
| Interim Events History | | |  | | |  |  |  |  |  |
| Assessment of Beta-Blocker Usage | | | | | | |  |  |  | |

| Legend | |
|---|--------------------------------------|

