6.1.1 Baseline In-Person Visit

- Informed consent
- Randomization
 - Eligible subjects will be randomly assigned to into Arm 1 (ABAB) or Arm 2 (BABA) with a 1:1 ratio using a computer-generated randomization scheme developed by the data manager. Arm 1 will be on an On-Off-On-Off (ABAB) drug scheme, while Arm 2 will be Off-On-Off-On (BABA)
- Demographics
- Medication Inventory
- Baseline beta-blocker use
- Physical Exam, including vital signs
- Central blood pressure assessment via the UScom BP+ device
 - This device measures central and brachial blood pressure and blood pressure waveforms at the heart, as well as in the arm.
- Electrocardiogram
- Blood draw for Troponin & NT-proBNP
- Blood draw for future research
- Six-Minute Walk Test
- Exercise test used to assess aerobic capacity endurance. The distance covered over 6 minutes is used as the outcome by which to compare changes in performance capacity.
- Short Physical Performance Battery
 - Combines the results of gait speed, chair stand and balance tests as a predictive tool for possible disability and can aid in the monitoring of function in older people
 - Gait Speed: assesses the subject's lower extremity function
 - Chair Rise: assesses core strength
 - Balance Test: assess the subject's ability to stand unassisted without the use of a cane or walker
- Qualitative interview on understandability of study purpose and design
- Typology Questionnaire
- Health Literacy Questions
- Number Literacy Questions
- Short Graph Literacy
- EQ5D Visual Analogue Scale
- PROMIS-29
- PROMIS-SF 6A
- PROMIS-Sexual Function
- KCCQ-12
- Decision Making Outcomes Questionnaires
 - Decision Conflict Scale
 - Decision Conflict Subscale
 - Patient Activation Measure (PAM) Survey
 - Shared Decision Making Questionnaire
 - Revised Patient Attitude Towards Deprescribing Questionnaire (rPATD)

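### The carry-over term in the main model turns the peak VO2 crossover into a Period 1 comparison of 8 versus 8 patients and removes the power the plan relies on

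*Combined protocol and SAP*

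**What the plan says.** - **Model (section 12.4.1).** On and Off are compared with a general linear mixed model in which "fixed effects of BB, period effect (Period 1 or Period 2) and carry-over effect will be included", together with a patient-level random intercept. The peak VO2 item in that section calls for a mixed model and gives no different specification.
- **Peak VO2 data.** Section 3.1 schedules a "non-invasive cardiopulmonary exercise test (CPET) at the end of period 1 and at the end of period 2", and footnote 2 to the Schedule of Assessments (6.1) confirms "Cardiopulmonary Test to occur only at the end of Period 1 and Period 2". Section 1.2.1 lists peak VO2 as co-primary.
- **Size and allocation.** "This study will enroll 16 subjects" (synopsis). They are "randomly assigned to into Arm 1 (ABAB) or Arm 2 (BABA) with a 1:1 ratio" (section 6.1.1), nominally 8 per sequence.
- **Power (section 12).** The plan claims "80% power to detect a within-patient difference of 1.1 standard deviations in the four outcomes", at an alpha of 1.67%. It does not say which standard deviation is meant.
- **Washout (section 3.1).** Periods last up to 6 weeks, "permitting sufficient time for up-titration and onset of drug action, and down-titration and washout".
- **A second model.** For the patient-reported statistics to be shared with subjects, sections 12 and 12.4.1 describe a model with "period effect (1, 2, 3, 4 etc.)" and no carry-over term.

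**The concern.** The reason for a crossover with 16 patients is that each patient is compared with themselves, and the power statement is written in those terms. A two-period AB/BA layout has no information to spare for a carry-over parameter. Fitting one leaves only the between-patient comparison in Period 1 to estimate the treatment effect.

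Peak VO2 would then be analysed as a small parallel-group trial while being described, and powered, as a crossover. The longer ABAB/BABA sequences lose less, but the previous treatment is always the opposite of the current one, so carry-over is nearly aliased with treatment there too. Coding period only as 1 or 2 also does not fit outcomes measured over the 2 to 6 periods a patient may complete.

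**Working it through.** **Inputs.** From the documents: 16 patients, 1:1 (8 and 8); two peak VO2 measurements per patient; effect 1.1 SD; two-sided alpha 5%/3 = 1.67%. Assumed: the correlation ρ between a patient's two measurements, which the documents do not give, shown from 0 to 0.9; constant between-patient SD σ; complete data.

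**1. The plan's own power figure.** Take 1.1 as the SD of the paired difference. The noncentrality is 1.1 × √16 = 4.4. With 14 df the critical value is 2.718 and power is 93.8% (94.2% with 15 df). The stated 80% does not reproduce at N = 16 on this reading. It is matched with about 12 patients, or if 1.1 is in between-patient SDs with ρ near 0.25 (79.5%). The documents state neither.

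**2. Cell means.** Code On = +½ and Off = −½. Let τ be the On-Off effect and λ the carry-over of the previous treatment.

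| | Period 1 | Period 2 |
|---|---|---|
| AB (On first) | μ₁ + τ/2 | μ₂ − τ/2 + λ/2 |
| BA (Off first) | μ₁ − τ/2 | μ₂ + τ/2 − λ/2 |

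The AB−BA difference is τ in Period 1 and −τ + λ in Period 2. When λ is fitted, it absorbs the Period 2 difference, so only Period 1 estimates τ. Generalised least squares confirms this. The weights on (Period 1, Period 2) are (+½, −½) for AB and (−½, +½) for BA without carry-over. With carry-over they are (+1, 0) and (−1, 0).

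**3. Standard errors.**
- Without carry-over: σ√[2(1−ρ)/16].
- With carry-over: σ√(1/8 + 1/8) = 0.50σ at every ρ.
- Variance ratio: 0.25 ÷ [(1−ρ)/8] = 2/(1−ρ).

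**4. Power for peak VO2.** If 1.1 is in paired-difference SDs, the raw effect is 1.1 × √[2(1−ρ)] σ. Dividing by 0.50σ gives the noncentrality on 14 df. For example, at ρ = 0.5 it is 1.1/0.50 = 2.2.

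| ρ | SE without (σ) | SE with (σ) | Variance ratio | Power without | Power with |
|---|---|---|---|---|---|
| 0 | 0.354 | 0.50 | 2.0 | 94% | 65% |
| 0.3 | 0.296 | 0.50 | 2.9 | 94% | 48% |
| 0.5 | 0.250 | 0.50 | 4.0 | 94% | 34% |
| 0.7 | 0.194 | 0.50 | 6.7 | 94% | 20% |
| 0.8 | 0.158 | 0.50 | 10 | 94% | 13% |
| 0.9 | 0.112 | 0.50 | 20 | 94% | 7% |

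If 1.1 is in between-patient SDs, the noncentrality with carry-over is 2.2 at every ρ, so power is 34% throughout. Without carry-over it is 65% at ρ = 0 and 94% at ρ = 0.5.

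The difference detectable with 80% power when carry-over is fitted is 1.81σ. Detecting 1.1σ between patients would need 19 per group.

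**5. Four periods (ABAB/BABA, 8 per sequence).** Adding carry-over moves the SE from 0.177σ to 0.399σ at ρ = 0.5, from 0.137σ to 0.315σ at 0.7, and from 0.112σ to 0.259σ at 0.8. The variance ratio is 5.1 to 5.4. For an effect of 1.1 paired-difference SDs, power with carry-over is about 61%, 59% and 58% (43 df).

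**6. Sequence term instead.** Replacing carry-over by a sequence effect in AB/BA leaves the SE at 0.194σ for ρ = 0.7, the same as with neither term. Fitting both carry-over and sequence in AB/BA makes the model singular.

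**The case against.** The strongest reply is that the plan gives no coding for its carry-over effect. In a two-period crossover, carry-over and sequence are confounded, and some analysts enter a sequence term under that name. If that was meant, no power is lost. But carry-over in its ordinary sense is the first-order term, and a sequence term does not adjust the treatment effect for carry-over. The text needs correcting on either reading.

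Other points stand in part:

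- **The size is conditional.** ρ is an assumption, and the 20% and 13% figures hold only if 1.1 refers to the paired-difference SD. The direction of the loss depends on neither.
- **Scope.** Full collapse is confined to two-period data: peak VO2, patients who stop after Period 2, or any analysis limited to Periods 1 and 2. With four periods the loss is large but partial.
- **Period coding.** The 1, 2, 3, 4 coding belongs to a different model, and limiting the endpoint model to Periods 1 and 2 may have been deliberate. If so, the plan should say so.
- **Washout is not a guarantee.** The rule of using the last two weeks is written for vitals, step count and patient-reported outcomes, not for SPPB or peak VO2, although those two are measured at period end. In Table 4 some examples reach Off only in week 5.
- **Pilot status.** Section 12 calls power modest and disclaims an efficacy goal, but the disclaimer is attached to the feasibility objective. The same section claims 80% power for the quantitative outcomes and wants their estimates for a larger trial.

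**Conclusion.** The concern holds and must be fixed. Under the ordinary meaning of carry-over and with complete data, the model in section 12.4.1 estimates the peak VO2 effect from Period 1 alone, 8 patients against 8. The standard error is 2.0 to 3.2 times that of the within-patient analysis for ρ between 0.5 and 0.8, and 1.4 times even at ρ = 0. Power is at most 65% on the paired-difference reading of 1.1 SD and 34% on the between-patient reading, so it is below the stated 80% for every ρ ≥ 0.

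These figures assume exact 8:8 balance, although no blocking is described, and every CPET performed, although remote visits omit it. Departures from either would reduce precision further.

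**What to change.** In section 12.4.1:

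1. Remove carry-over from the primary model. Use On/Off, period as a categorical factor, and patient random effects. A sequence term may be added at no material cost.
2. Define period over all completed periods for outcomes measured beyond Period 2, and over Periods 1 and 2 for peak VO2. If restricting every outcome to two periods was intended, state that and the reason.
3. Report a carry-over model only as a sensitivity analysis, with its coding written out. For peak VO2, say plainly that it amounts to the Period 1 between-patient comparison.
4. In section 12, state which standard deviation the 1.1 refers to, so that the power statement matches the model.

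The cost is SAP wording; no visit, measurement or sample size changes. The statistical price is that carry-over surviving the taper and washout goes unadjusted: in the two-period model the estimate becomes τ − λ/2, a bias of half the carry-over effect. If the two-period restriction was deliberate, using all completed periods also enlarges the analysed data, and the number of periods depends on each patient's own decision, so that choice should be declared.
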